Full title:

A Multicenter Randomized Controlled Trial Assessing the Efficacy of Antimicrobial Prophylaxis for Extracorporeal Shock Wave Lithotripsy on Reducing Urinary Tract Infection

Brief Title:

Antibiotic Prophylaxis Before Shock Wave Lithotripsy (APPEAL)

1. Objectives & Specific Aims

The lifetime risk of developing nephrolithiasis has been reported between 1-15%, with a prevalence of approximately 5% in North America. SWL is a very common first line treatment for ureteral and renal calculi. One of its benefits is that it has few complications. However, infection remains an important complication of the procedure. Because of this risk the American Urological Association recommends pre-SWL antibiotics for all patients. However, this approach is controversial because studies to date are of poor quality and there is concern over antibiotic resistance. Therefore the European Association of Urology recommends only selective use of antibiotics pre-SWL. To resolve this conflict and establish the most appropriate strategy for Ontarians, we propose to perform a randomized trial comparing pre-procedure antibiotics to no antibiotics among patients who undergo SWL.

The primary goal of our study is to evaluate the impact of antibiotic prophylaxis on the rate of bacteriuria, symptomatic UTI, pyelonephritis and urosepsis among patients with sterile urine undergoing SWL. Our secondary goal is to determine pre-procedural characteristics that can define patient subgroups with the greatest benefit from prophylactic antibiotics.

We hypothesize that a single dose of intravenous ciprofloxacin immediately prior to SWL will decrease the relative incidence of bacteriuria, symptomatic UTI, pyelonephritis and urosepsis by 60% or greater. Additionally, we anticipate that pre-operative patient and stone characteristics such as age, gender, history of UTI, patient comorbidities, stone size, location, may be predictive risk factors that can be used to optimize patient selection for pre-operative antibiotic use.

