To test this hypothesis we propose to conduct a large ($n \geq 1350$), multicenter prospective randomized, blinded, placebo controlled trial (RCT). We recognize that our primary question may be difficult to study due to low rates of symptomatic UTI post-SWL. Therefore we propose to undertake this RCT in two phases. The Vanguard phase, which will consist of up to one fourth of the total study population, will be used to determine feasibility. Feasibility will be assessed in terms of rates of patient recruitment, percent adherence to randomization, percent data completion and percent loss to follow-up. Using pre-defined criteria, if the study is deemed to be feasible without major protocol alterations, the Vanguard phase patients will be included in the larger study. Patient recruitment will then continue until our target population size has been reached. Should the Vanguard phase be unable to demonstrate feasibility, then the available data will be analyzed, which will still provide the largest and most methodologically robust dataset available in the literature at this time.

The results of our RCT, whether positive or negative, will contribute significantly to the existing literature as it will provide the strongest Level 1 evidence available for future meta-analyses and guidelines. If the study results show a benefit to antibiotic use the expected impact on patient care will be to reduce rates of infectious complications. Furthermore, our study will allow for a more selective use of antibiotics as several important predictors of infectious complications will be elucidated through a multivariate analysis. Conversely, a null study will provide the strongest evidence against routine prophylaxis in the literature to date and potentially decrease the unnecessary use of antibiotics among patients undergoing SWL. Consequently, this would represent a cost savings to the healthcare system and may reduce the risk antibiotic resistant bacteria.

2. Background, Rationale & Present State of Knowledge

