Based on the existing literature, a prominent area of concern that emerges is how to define a positive urine culture and how to assess for symptomatic urinary tract infection. Previous studies have used a variety of bacterial concentration cutoffs for the definition of a positive culture¹³. We will use the most common historically accepted definition ($\geq 10^5$ CFU/ml) to define a conservative estimate of bacteriuria for the primary and secondary endpoints of our study³⁶. To define a symptomatic UTI we will capture symptoms in two different ways. We will use a predefined questionnaire in a systematic way asking patients to identify both the presence and absence of lower urinary tract symptoms as well as to quantify the magnitude of these symptoms on a scale from 0 to 5. We recognize that the passage of stone debris or presence of stent can cause lower urinary tract symptoms, but believe that appropriate randomization over a sufficiently large cohort will control for this confounder.

In addition we will evaluate the IPSS score as a quality of life measure for lower urinary tract symptoms post-SWL. We believe this is important as symptoms of UTI related to SWL may worsen IPSS scores and correlate to decreased quality of life. It is therefore of benefit to evaluate whether pre-operative antibiotic use can impact on this aspect of patient care. Unfortunately there have not been any systematically validated questionnaires that can be used to diagnose urinary tract infections among men and women. The urinary tract infection symptom assessment questionnaire (UTISA) has been validated to track resolution of UTI symptoms among symptomatic women. However it is not diagnostic nor has it been validated in men³⁷. We have chosen to use the IPSS, as it has been widely validated for the description of lower urinary tract symptoms in men³⁸⁻⁴⁰. It IPSS has also been frequently used to define lower urinary tract symptoms in women in several clinical contexts⁴¹⁻⁴⁴. We recognize that it has not been shown to be useful in the evaluation of bladder outlet obstruction in women⁴⁵, a pathology that we are not assessing in our RCT.

3. References

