Patients routinely undergo neuroleptic anesthesia during SWL at participating centers, as such it is usual care for the patient to have a saline infusion during SWL. The choice of whether or not to administer antibiotics is usually at the discretion of the attending urologist, as there is no established standard of care. For the duration of the study, participants will be mandated to receive treatment in accord with randomization. However the attending urologist will retain the ability to break protocol in accord with their clinical judgment. Any break in protocol will be recorded as such but the data will be analyzed on an intent-to-treat basis. Ciprofloxacin was chosen as the study antibiotic as it is commonly used in everyday practice, has been used in previous RCTs on antibiotic prophylaxis pre-SWL³¹ and demonstrates a good sensitivity pattern to community acquired infections. Patients will undergo SWL with a maximum of 3000 shock waves (SW) for kidney stones and up to 4500SW for ureteric stones. Additional clinical parameters such as presence of double J, Stone characteristics and renal insufficiency will be recorded at the time of SWL by the dedicated research staff.

Patients will be asked to provide two urine samples for analysis. The first will be prior to SWL within 1 month of the procedure. On the day of procedure the patient will also complete baseline documentation. After the procedure, patients will complete follow-up documentation and a second urine culture. Urine cultures will be submitted to the laboratory or hospital most convenient for the patient at 7-14 days post-SWL and results will be forwarded to the regional site. We allow the patient to submit a urine culture at their usual laboratory in an effort to minimize the burden for the patient participating in the trial and to facilitate capture of follow-up data. This approach may be essential to capture data from patients referred from an outside institution, which may represent a significant commute. An additional advantage of this approach, in contrast to mandating the use of a central laboratory, is that it may better reflect the usual pattern of patient behavior when seeking follow-up for urinary tract symptoms post-SWL. We recognize that there may be differences in culture protocol between laboratories but we feel that these are more representative of actual practice and as such support the generalizability of the study.

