Data acquisition will be continuously monitored, with regular audits to assure that data from patients who have not complied with follow-up are obtained. Patients will be asked to provide a urine sample and complete and mail the follow-up form on post-operative day 7. If the follow-up questionnaire has not been received by post-operative day 10 patients will receive a reminder phone call. A second envelope will be sent containing a requisition for urine culture and follow-up questionnaire when necessary.

Our primary outcome will be a composite endpoint comprised of:

- Positive post-SWL urine culture ($\geq 10^5$ CFU/ ml), symptoms of cystitis (defined as new onset burning sensation or pain with voiding, frequency, urgency), or pyelonephritis or urosepsis (hospital admission with fever ≥ 38.5 C).

Our secondary outcomes will be:

Version 8.1 Last modified August 21, 2018

- Bacteriuria at 7-14 days post-SWL ($\geq 10^5$ cfu/ml)
- Symptoms of cystitis (new onset burning sensation or pain with voiding, frequency, urgency)
- Pyelonephritis or urosepsis (hospital admission with fever $\geq 38.5^\circ\text{C}$)
- Change in IPSS score at 2 weeks (reported as a numerical value)

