The power calculation for this protocol was performed using Stata v.10.1 (StataCorp, College Station, TX). Reported incidence of bacteriuria, symptomatic UTI and pyelonephritis post-SWL vary greatly¹⁰⁻¹³. Therefore, to estimate the expected incidence of our primary outcome, we used the incidence of bacteriuria reported in the AUA Best Practice Statement on antibiotic prophylaxis¹⁷. In the AUA statement, patients undergoing SWL in the placebo arm of trials assessing antibiotic prophylaxis had a 5.7% rate of bacteriuria as compared to 2.1% among those who received prophylaxis. This represented an absolute difference of 3.6% (a 60% relative risk reduction). Therefore to achieve a power of 90% to find an absolute difference of 3.6% in the occurrence of bacteriuria, with a significance level of $p < 0.05$, 661 patients will need to be recruited in each arm for a total of 1,322 patients. Accounting for 10% loss to follow-up, the total required will be 1454, or approximately 1500 patients. Assuming that 25% of patients screened will either refuse to be randomized or will meet one of the pre-defined exclusion criteria, a total of 2000 patients will need to be screened in order to randomize 1500 patients.

Statistical analysis

Once all study data has been collected, we will report the patient characteristics at enrollment, and the primary and secondary outcomes. Comparison between RCT outcomes will be performed using Fisher's exact test for binary outcomes and Student's t-test for continuous outcomes. Lost to follow-up will be accounted for according to intent to treat analysis. Patients who are lost to follow-up will be considered not to have bacteriuria, cystitis, pyelonephritis or urosepsis and a change in IPSS of zero. This will allow us to accomplish the primary objective: to determine the impact of antibiotic prophylaxis on our primary and pre-defined secondary endpoints. We will also perform a univariate and multivariate analysis using a stepwise logistic regression model to assess predictors of our primary

outcome. This will allow us to better characterize the impact of pre-SWL antibiotic use in the context of other known risk factors for UTI.

Strengths and weaknesses of study design

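### The predictor model is fitted only to a composite that culture-negative symptoms can meet, so factors that cause mechanical symptoms can be reported as predictors of infection

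*Combined protocol and SAP*

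**What the plan says.** Section 4, Statistical analysis, plans a "univariate and multivariate analysis using a stepwise logistic regression model to assess predictors of our primary" outcome. No other dependent variable is given for the predictor analysis.

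The primary outcome in Section 4 is a composite. Besides a positive culture after SWL it lists "symptoms of cystitis (defined as new onset burning sensation or pain with voiding, frequency, urgency), or pyelonephritis or urosepsis". No culture result is attached to the symptom component, and symptoms of cystitis appear again as a secondary outcome of their own, also without a culture requirement.

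Section 2 states: "We recognize that the passage of stone debris or presence of stent can cause lower urinary tract symptoms". Its answer is that the authors "believe that appropriate randomization over a sufficiently large cohort will control for this confounder".

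Section 1 sets out what the predictor analysis is for. Patient and stone characteristics, with stone size and location among those named, "may be predictive risk factors that can be used to optimize patient selection for pre-operative antibiotic use". It also says that "several important predictors of infectious complications will be elucidated through a multivariate analysis". Stent status is not among the characteristics named there, but Section 4 says: "Additional clinical parameters such as presence of double J, Stone characteristics and renal insufficiency will be recorded".

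**The concern.** The model answers one question and its results will be described as answering another. It identifies who meets the composite, which includes patients whose only event is burning, frequency or urgency with a negative culture. Section 1 presents the result as showing who gets an infectious complication.

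The gap matters because the plan itself names a non-infectious cause of the counted symptoms, and that cause is tied to candidate predictors. A larger or differently placed stone may shed more debris and so cause more symptoms without any change in infection risk. Randomization balances debris and stents between ciprofloxacin and placebo. It does nothing to separate the mechanical from the infectious effect of a stone factor, because stone factors are not randomized.

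At stake is the stated secondary goal. Advice on selective prophylaxis could rest on factors that mark mechanical symptoms, while genuine infection predictors are diluted in the same model. The primary comparison of arms is not affected by this point.

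**Working it through.** **Planning figure.** The plan gives no figure for the predictor analysis. The nearest is the sample size, which supplies the bacteriuria rates used below: 5.7% on placebo and 2.1% on prophylaxis, 90% power, significance level 0.05 (taken as two-sided).

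- Uncorrected: n = [1.960·√(2·0.039·0.961) + 1.2816·√(0.057·0.943 + 0.021·0.979)]² / 0.036² = (0.5366 + 0.3494)² / 0.001296 ≈ 606 per arm.
- With continuity correction: (n/4)·[1 + √(1 + 4/(n·0.036))]² = 661 per arm, or 1,322 in total. This matches the plan.

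**Bacteriuria events.** In the 1,350 patients with complete data that the plan targets: 675 × 0.057 + 675 × 0.021 = 38.5 + 14.2 = 52.7, about 53.

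**Inputs that are assumptions.** The documents give neither the rate of culture-negative symptoms nor the prevalence of any candidate factor. I take a binary factor present in 10% or 20% of patients, with no effect on bacteriuria. Symptoms among non-bacteriuric patients occur at rate s0 without the factor and s1 with it. The plan states no entry threshold for the stepwise procedure, so a flag means p<0.05.

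**Formulas.** With b = (0.057 + 0.021)/2 = 0.039, the composite rates are p0 = b + (1 − b)·s0 and p1 = b + (1 − b)·s1. The chance of a flag is approximately Φ[(p1 − p0 − 1.96·SE0)/SE1], where SE0 is the pooled and SE1 the unpooled standard error of the difference.

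**Worked case, 5% and 10%, prevalence 10%** (135 patients with the factor, 1,215 without):

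- p0 = 0.039 + 0.961 × 0.05 = 0.0871; p1 = 0.039 + 0.961 × 0.10 = 0.1351.
- Odds ratio = (0.1351/0.8649)/(0.0871/0.9129) = 1.64.
- SE0 = 0.0262, SE1 = 0.0305. Chance of a flag = Φ[(0.0481 − 0.0514)/0.0305] = Φ(−0.108) = 46%.
- Composite events = 1,215 × 0.0871 + 135 × 0.1351 = 124, of which 1 − 52.7/124 = 58% are culture-negative.

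**All cases:**

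| Symptoms without / with factor | Composite OR | Flagged, formula (prevalence 10% / 20%) | Flagged, simulation (10–20%) |
|---|---|---|---|
| 2% / 3% | 1.18 | 8% / 10% | about 10% |
| 2% / 4% | 1.36 | 17% / 23% | 16–24% |
| 5% / 10% | 1.64 | 46% / 65% | 42–65% |
| 10% / 20% | 1.93 | 81% / 96% | 81–96% |
| 10% / 30% | 3.11 | about 100% / 100% | about 100% |

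The simulations fit a logistic model on arm and the factor. With bacteriuria as the dependent variable, the same factor is flagged in 3–5% of trials.

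**Dilution.** Now let the factor truly double the odds of bacteriuria and leave a 10% background of symptoms unrelated to it. In simulation the bacteriuria model detects it in about 51–69% of trials and the composite model in about 20–30%.

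**The case against.** **The effect may be small.** It rests on assumed symptom rates and prevalences. At 2% and 3% the flag rate is about 10%, not far above nominal. This stands. A reader might infer that such factors will be reported as infection predictors. The documents do not support that: they give no symptom rates, no prevalences and no fixed candidate list.

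**The stent is a weak example.** Patients who need a stent placed on the day of SWL are excluded, so enrolled stents are generally already in place. Symptoms must be of new onset, and a baseline questionnaire and IPSS are completed before the procedure. Section 1 does not name stent as a candidate. This largely stands, although the plan does not say how new onset is judged against baseline. It does not apply to stone size and location, which Section 1 names; debris symptoms arise after SWL and do count as new.

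**Components are reported separately.** Readers will see how much of the composite is symptom-driven. True, but Section 4 gives the purpose as checking that the treatment effect is concordant across components. No predictor model is planned for any single component.

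**Bacteriuria alone is a poor replacement.** It yields few events and omits culture-negative cystitis that may matter clinically. This is a fair argument against dropping the composite model, which a reader might think follows from the point. It is no argument against adding a second model.

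**Conclusion.** The concern holds in a limited form. The predictor model has one dependent variable, that variable can be met without evidence of infection, the plan concedes the non-infectious route, and the randomization defence does not reach non-randomized predictors. Stone size and location, and to a lesser degree a pre-existing stent, can therefore be reported as predictors of infectious complications when they only cause mechanical symptoms.

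The false-flag rate lies anywhere from about 10% to about 100% across the assumed range, against 3–5% for a bacteriuria model. Where in that range the trial would fall cannot be determined from the documents. The figures also rest on a single binary factor, p<0.05, and a model with arm and that factor only; the planned stepwise selection over several correlated candidates could behave differently.

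The point concerns a secondary goal, and nothing here calls the primary treatment comparison into question. It should be corrected because the correction is cheap.

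**What to change.** In Section 4, Statistical analysis, add a second predictor model beside the planned one, with a culture-based dependent variable: bacteriuria at or above 10^5 CFU/ml at 7–14 days, or bacteriuria plus hospital admission with fever. Keep the composite model.

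State that factors found only in the composite model are described as predictors of the composite, and that statements about predictors of infection or about selective antibiotic use rest on the culture-based model.

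The cost is a sentence or two; the cultures and admissions are already collected. The drawback is precision. About 53 bacteriuria events at the planning rates support only a few candidate predictors, so the list should be short and fixed in advance, and estimates will be imprecise. By the simulation above, even a true odds ratio of 2 would be missed in roughly a third to a half of trials.

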The proposed study will be carried out in two phases. The initial Vanguard phase will assess the feasibility of the trial in terms of rates of patient recruitment, percent adherence to randomization, percent data completion and percent loss to follow-up. Pre-defined criteria to determine feasibility will be a rate of randomization of ≥ 16 patients per week, with 95% adherence to randomization and an overall rate of $\geq 90\%$ data collection at 3 weeks post-SWL, and an overall loss to follow-up of $\leq 10\%$. These parameters will be assessed weekly throughout the Vanguard period. This phase of the study will continue until all target parameters have been met for 3 consecutive weeks and a minimum of 200 patients have been randomized. If these parameters are met then the Vanguard phase will be interpreted to have demonstrated feasibility and patient recruitment will continue until complete data for ≥ 1350 patients has been collected. Alternatively, the Vanguard phase may be concluded when a maximum of 300 patients or a six month period from study start date has elapsed or a modification to number of sites accruing may be considered. If the Vanguard phase fails to demonstrate feasibility, and we judge that this indicates that a significant protocol modification is needed we will close the trial and analyze available data. The data would be analyzed in accordance with pre-defined methodology and would be submitted for publication. Importantly, even if the Vanguard phase does not show feasibility, it would still provide the largest cohort of high quality data available in the literature and as such would still be an important contribution to the current state of knowledge.

The study centres, Helsinki University Hospital, University of Western Ontario St Joseph's Hospital, Université de Sherbrooke, Pontifical University Catholic of Campinas, Rede D'Or Sao Luiz, and King Abdulaziz University are each academic institutions with dedicated research staff. We estimate that total of 2000 patients will need to be screened in order to acquire complete data for 1350 patients. Accounting for a 10% dropout, up to 1500 patients may need to be randomized. Eligibility criteria include patients older than 18 years presenting for SWL who do not meet one of the pre-defined exclusion criteria. Exclusion criteria are:

- Pre-SWL urine analysis positive for nitrites
- Pre-SWL urine culture reveals $>10^5$ CFU/ml of bacteria (positive urine culture)

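### Stepwise selection on about 53 expected events will, if predictors are of modest strength, usually give an incomplete predictor list with inflated odds ratios; one fixed, fully reported model avoids the selected estimates

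*Combined protocol and SAP*

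**What the plan says.** Section 4, Statistical analysis, plans a "univariate and multivariate analysis using a stepwise logistic regression model to assess predictors of our primary" outcome. It adds: "This will allow us to better characterize the impact of pre-SWL antibiotic use in the context of other known risk factors for UTI". It gives no candidate list, direction of selection, entry or removal threshold, coding, shrinkage or validation. It does not say whether treatment is forced into the model.

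Section 1 makes it the secondary goal to define the subgroups that gain most from prophylaxis, and names as possible predictors "pre-operative patient and stone characteristics such as age, gender, history of UTI, patient comorbidities, stone size, location". The same section says that the multivariate analysis will bring out several important predictors and so permit more selective antibiotic use. Section 4 also has double-J stent, stone characteristics and renal insufficiency recorded at the procedure.

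No event count is given for this model. The only planning rates are in Section 4, Power and sample size calculation: "a 5.7% rate of bacteriuria as compared to 2.1% among those who received prophylaxis". They stand in for the composite: "to estimate the expected incidence of our primary outcome, we used the incidence of bacteriuria". The limitations discussion calls the IPSS exploratory but attaches no such caution to this regression.

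**The concern.** This regression is the only analysis described for the secondary goal, and its output is meant to guide who receives antibiotics. Univariate screening followed by stepwise search keeps a term only when its estimate happens to be large relative to its standard error. With few events, a modest true effect passes that filter mainly when chance has exaggerated it. The usual p-values and confidence intervals take no account of the filter. A reader of the final model would see a short list of apparently strong predictors, with no view of the factors that were dropped or how imprecisely they were estimated.

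**Working it through.** **1. The plan's own figure.** Inputs: 5.7% v 2.1%, two-sided 0.05 (sidedness is not stated), 90% power.
- Uncorrected: n = [1.96√(2×0.039×0.961) + 1.2816√(0.057×0.943 + 0.021×0.979)]² / 0.036² = 605.6.
- Continuity-corrected: (605.6/4)×[1 + √(1 + 4/(605.6×0.036))]² = 660.03, rounded up to 661. This matches "661 patients will need to be recruited in each arm for a total of 1,322 patients".

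**2. Expected events.** Section 4 screens "in order to acquire complete data for 1350 patients", or 675 per arm at equal allocation.
- 675×0.057 + 675×0.021 = 38.5 + 14.2 = 52.65.
- Randomising about 1500 adds none, because patients lost to follow-up are counted as free of the outcome.

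**3. Candidates (inferred).** Six from Section 1, plus double-J stent and renal insufficiency from Section 4, plus treatment arm, make nine. 52.65/9 = 5.9 events per candidate, and fewer if comorbidities or location take several terms. Eight treatment interactions would make 17 terms: 52.65/17 = 3.1.

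**4. Range for the events.** Section 2 reports bacteriuria of 8-23%. Taking that as the placebo rate with the same rate ratio (2.1/5.7 = 0.368):
- 675×0.08×1.368 = 74 events (8 per candidate).
- 675×0.23×1.368 = 212 events (24 per candidate).
- Cystitis symptoms in the composite could add more.

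**5. Why kept odds ratios are inflated.** For a binary factor of prevalence q and E events among N patients, SE(log OR) ≈ 1/√[E(1−E/N)q(1−q)]. A term reaches p<0.05 only if its OR exceeds exp(1.96×SE). The prevalences are assumptions.
- E = 52.65, q = 0.4: SE = 0.287, threshold OR 1.75. A true OR of 1.5 passes with probability about 29%.
- E = 52.65, q = 0.2: SE = 0.351, threshold OR 1.99.
- E = 212.4, q = 0.4: SE = 0.153, threshold OR 1.35. A true 1.5 passes with probability about 76%.

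For noise, five independent null factors tested at 0.05 give 1 − 0.95⁵ = 23% with at least one kept.

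**6. Simulation.** 1350 patients, about 53 events, treatment plus eight candidates, backward selection at p<0.05. True ORs were 1.5, 2.0 and 1.5, with five noise variables. Ranges are over runs with different assumed prevalences.

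| Result | Stepwise | Fixed model, all terms reported |
|---|---|---|
| Exact true set found | 3-5% | not applicable |
| At least one noise variable kept | 20-21% | not applicable |
| A true OR 1.5 factor kept | 20-29% | always reported |
| Median OR for a true 1.5 | 2.0-2.2 when kept | 1.46-1.51 |
| Coverage of 95% CI (OR 1.5 factors) | 86-93% when kept | 95-96% |

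**7. Sensitivity (backward selection, p<0.05 unless stated).**
- Mixed true ORs 1.3/1.5/2.0/2.5, 53 events: exact set 1.3%; mean kept ORs 1.98/2.13/2.48/2.81.
- True ORs all 2.0, 53 events: exact set 36%, 24% and 16% with two, three and four true predictors; kept OR 2.3-2.4.
- Three true ORs of 2.5, 53 events: exact set 47-53%; kept OR 2.7-2.8. Three of 3.0: 70%; kept OR 3.13.
- True ORs 1.5/2.0/1.5, 106 events: exact set 13%. At 212 events: 35-38%; kept ORs 1.59/2.03/1.57; a noise variable in 24% in one run.
- Retention at p<0.157, 53 events: a noise variable in 47-57%. The plan sets no threshold.

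**The case against.** **The harm comes from few events and a 0.05 cut-off, not from the stepwise search.** This stands. When the pre-specified full model was read at p<0.05 in the same simulations, it did no better. In one run the exact set was found in 3.9% of trials (stepwise 3.7%), in another 4.5% (stepwise 4.8%). A noise variable appeared in 20.7% under both. Median ORs of the significant true terms were 2.04/2.44/2.08 against 2.01/2.42/2.07. The gain therefore lies in reporting every coefficient without selection. A reader might infer that dropping stepwise would reveal the right predictors; it would not.

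**The list would be mostly wrong.** A reader might infer this, but the numbers do not support it. About 79% of simulated trials kept no noise variable, and in one run only 17% of retained predictors other than treatment were false. The main fault is omission.

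**The procedure could discard treatment.** The plan never says that treatment is open to removal. If it were, it would be lost in 6-7% of trials at 53 events. The full model finds it non-significant about as often (6.6% against 6.9%), which is unsurprising for a comparison planned at 90% power. The treatment effect is in any case tested by Fisher's exact test.

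**Fifty-three events may be too few.** This is fair. The rates are for bacteriuria alone, while the composite also counts cystitis symptoms, which Section 2 accepts can come from stone debris or a stent. The range of 74 to 212 belongs with the figure. Still, 53 is what the plan's own sample size implies.

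**Nine candidates and the predictor strengths are not in the plan.** Also fair. Section 1's list is open-ended, the Section 4 variables are only said to be recorded, and no predictor odds ratios are given.

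**Conclusion.** The concern holds, conditionally, for the secondary predictor analysis only. At the planning rates there are about 53 events for roughly nine inferred candidates. If true predictors have odds ratios of 1.5 to 2.0, the selected list will usually be incomplete and will include a false predictor in about one trial in five at p<0.05. A true 1.5 will appear as about 2.0 to 2.2, with nominal 95% intervals covering 86-93%. With odds ratios of 2.5 to 3 the inflation falls to about 4-13% (3.13/3.0 to 2.83/2.5), and near 212 events a true 1.5 is reported as about 1.6. The predictor strengths, prevalences and retention threshold are assumptions. The primary comparison is untouched. The change should be made because it is cheap and the output is meant to inform selective antibiotic use, but the trial's main conclusion does not depend on it.

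Separately, a main-effects model shows who is at higher risk. It does not test whether the relative effect of prophylaxis differs between patients, which the stated goal of finding those who benefit most requires.

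**What to change.** In Section 4, Statistical analysis:

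- Remove the univariate screen and stepwise selection.
- Before unblinding, fix one logistic model with treatment forced in and a short covariate list with stated coding. Draw the list from Section 1 (including comorbidities) and the procedure-day variables in Section 4.
- Report all coefficients with confidence intervals, not a list of significant terms, and label the analysis exploratory.
- For the question of who benefits most, name a few treatment-by-factor interactions in advance, report their estimates and intervals, and label them exploratory too.
- State the expected events, about 53 with a range of about 74 to 212 under the Section 2 rates, so that the list length can be judged against them.

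Penalisation and bootstrap optimism correction are optional: the unpenalised fixed model was already nearly unbiased in simulation.

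Cost: wording and a few hours of analysis, with no new patients or data. The drawbacks are that the covariate list must be settled in advance and that the report will show more imprecise terms.
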